Nevertheless, the effectiveness and tolerability of finerenone in patients with non-diabetic chronic kidney disease (CKD) have not yet been clearly established [25]. The design of this study aims to determine whether the renal protective benefits of finerenone also apply to non-diabetic CKD patients, including those with an estimated glomerular filtration rate (eGFR) below 15 ml/min/1.73m² [26]. To our knowledge, our investigation is pioneering in assessing the therapeutic potential and safety profile of finerenone for this specific patient group [27].

II. Research Objective

To assess the progression of kidney disease in non-diabetic CKD patients following the use of finerenone, and to analyze the safety profile of finerenone.

III. Research Content

Investigate the changes in renal function in non-diabetic CKD patients after the administration of finerenone.

Analyze the relationship between the use of finerenone and cardiovascular events.

Evaluate the safety of finerenone treatment.

IV. Research Methodology

(A) Study Design

This project is a single-center, retrospective cohort study.

(B) Study Population

The study population comprises patients who were hospitalized for treatment or followed up on an outpatient basis in the Department of Nephrology, the First Hospital affiliated with Harbin Medical University, starting from December 15, 2023. The baseline for the study is defined as the occasion when a patient with CKD (either as a primary or secondary diagnosis) was first admitted to the nephrology department for hospital treatment or an outpatient visit.

Inclusion criteria:

- (1) Patients who were hospitalized or followed up on an outpatient basis in the Department of Nephrology, the First Hospital affiliated with Harbin Medical University, starting from December 15, 2023;
- (2) Patients with non-diabetic kidney disease;
- (3) Patients with electronic medical records available.

Exclusion criteria:

- (1) Type 2 diabetes mellitus;

(2) Patients who refuse to participate.

(C) Study Variables

In accordance with the research objectives, the project will collect the following variables:

Baseline patient characteristics: including age, gender, stage of kidney disease, comorbidities, medication history, etc.

Use of finerenone: including dosage, duration of therapy, etc.

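### Entry and baseline are not tied to starting finerenone, and no rule separates new from existing users, so 'before' values can be on-drug and early harms can be missed.

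*Combined protocol and SAP*

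**What the plan says.** Section III sets two aims that depend on when treatment starts: "Investigate the changes in renal function in non-diabetic CKD patients after the administration of finerenone" and "Evaluate the safety of finerenone treatment".

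Section IV (B) fixes who enters. The first inclusion criterion is "Patients who were hospitalized or followed up on an outpatient basis in the Department of Nephrology" of the study hospital, from December 15, 2023. The others are non-diabetic kidney disease and "Patients with electronic medical records available". The exclusions are type 2 diabetes and "Patients who refuse to participate". Baseline is the occasion when a patient with CKD "was first admitted to the nephrology department for hospital treatment or an outpatient visit".

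Section IV (C) lists, among baseline characteristics, "stage of kidney disease, comorbidities, medication history, etc", and for exposure "Use of finerenone: including dosage, duration of therapy, etc". Safety data are all recorded adverse events, with no time window. Section IV (D) takes the data mainly from this hospital's own electronic record system. Section V describes finerenone dose and duration. It offers a paired t-test or Wilcoxon signed-rank test if renal function before and after treatment is to be compared, without defining the value that counts as before.

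**The concern.** A before/after comparison answers a question about starting a drug only if the first value precedes the drug. Entry here depends on place and calendar date, and the wording covers patients already in follow-up. Baseline depends on a nephrology contact. A patient whose finerenone began earlier, here or at another hospital, meets every criterion and may have been on the drug at the baseline visit.

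Two things are then at stake. The paired renal change for such a patient need not contain the start of treatment. And a patient still taking the drug at entry has tolerated it so far, while one who stopped early may never enter, or may enter without being recognised as a former user. Section I says that tolerability in non-diabetic CKD is not established, so the early treatment period is what readers of this study most need to see.

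**Working it through.** The plan states no figure on this point, so there is none to reproduce. The check has two parts: what the text requires, and how large the effect could be under stated assumptions.

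**1. Where a new-start rule could sit**

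| Place | Is it tied to starting finerenone? |
|---|---|
| Inclusion criteria, IV (B) | No: contact and date, diagnosis, records |
| Exclusion criteria, IV (B) | No: type 2 diabetes, refusal |
| Baseline, IV (B) | No: a nephrology admission or visit |
| Exposure and medication history, IV (C) | Collected, but no eligibility or analysis rule uses them |
| Safety data, IV (C) | No window relative to the first dose |
| Before/after test, V | Conditional; the before value is not defined |

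No section asks for a drug-free look-back or an eGFR before the first dose.

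**2. Two readings of the baseline sentence.** The word 'first' is not qualified.
- First ever in this department: baseline precedes any start made by the department. The problem shrinks largely to finerenone started elsewhere.
- First since December 15, 2023: any patient already under treatment at that date can be on the drug at baseline. The problem is wider.

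Under either reading, the hospital record alone does not settle who is new. For a drug started elsewhere, the first local prescription is a continuation.

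**3. Renal change.** Let p be the share of existing users among users (assumed; not in the documents). Let D be the mean change in new users.
- If the change occurs wholly at initiation and existing users change no further: observed = (1 − p) × D + p × 0 = (1 − p) × D. At p = 10%, 25% and 50% the factor is 0.90, 0.75 and 0.50.
- If the effect is on ongoing decline and is the same in both groups: observed = (1 − p) × D + p × D = D, so there is no dilution.
- If existing users are selected for tolerating the drug, their change may be more favourable than D, which moves the result the other way.

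The net sign is therefore not determined.

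**4. Safety.** Assume a treatment-limiting event in 10% of patients in the first quarter on the drug and 2% in each later quarter.
- New users at 12 months: 10 + 3 × 2 = 16%.
- Existing users over 12 months from entry: 4 × 2 = 8%.
- Reported risk = (1 − p) × 16 + p × 8:

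| p | Reported risk | Ratio to 16% |
|---|---|---|
| 10% | 14.4 + 0.8 = 15.2% | 0.95 |
| 25% | 12.0 + 2.0 = 14.0% | 0.875 |
| 50% | 8.0 + 4.0 = 12.0% | 0.75 |

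Compounding the quarterly risks instead of adding them gives 1 − 0.90 × 0.98³ = 15.3% and 1 − 0.98⁴ = 7.8%. The reported risks become 14.5%, 13.4% and 11.5%, with nearly the same ratios.

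**The case against.** The strongest reply is that the means to separate the groups are already in the data. Medication history and duration of therapy are listed variables, and all recorded adverse events are collected without a window that would shut out events before entry. This stands in part: separation is possible, and some earlier harms held in this hospital's records may be found. But no rule makes that separation. Events treated elsewhere, and early stoppers who never came to this department, are out of reach.

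A second reply is that a test of renal function before and after treatment, read plainly, needs an off-drug first value, so a user without one has no pair. That is a fair reading. The plan does not state it, however, and the only baseline it defines is the nephrology contact.

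A third is that existing users may be few. The documents neither confirm nor rule this out. Without a flag, the report could not show it either.

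A reader might go further and infer that early harms are certainly lost, or that finerenone will look more protective of the kidney than it is. The documents support neither. The first fails because adverse events have no window. The second fails because dilution and selection of tolerant patients can pull in opposite directions, and an effect on ongoing decline need not be diluted at all.

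**Conclusion.** The point holds in this form: eligibility and baseline are not anchored to starting finerenone, and no planned rule distinguishes new from existing users. As written, the plan can place on-drug values at baseline and can leave out harms or stopping before entry. The safety estimate would then tend to be too low for patients starting the drug; the direction for renal change is open.

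The size is conditional. With 10% to 50% existing users, a change occurring wholly at initiation would show at 90% to 50% of its value. An assumed 16% risk would be reported as 15.2% to 12.0%. The share, the event rates and the absence of further change in existing users are all assumptions, and none comes from the documents. The actual share also depends on which reading of 'first' applies. The matter should be settled before further analysis, since Section VIII reports that 43 cases have already been organized and looked at.

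**What to change.** In Section IV (B):
- Restrict the main before/after renal analysis and the main safety analysis of users to new users. Define these as patients with no finerenone in the recorded medication history or in the hospital system before their first recorded finerenone prescription. That prescription becomes their start date.
- Require at least one eGFR before that date.
- Classify patients with missing medication history separately.
- State how many users are existing users, and report them separately and descriptively.
- If a comparison with non-users is made, apply the same no-prior-finerenone condition to them.

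Prior use of other mineralocorticoid receptor antagonists can be examined in an optional sensitivity analysis.

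The change needs protocol wording and a filter on variables already listed. It has two costs. The rule is only as good as the recorded history, whose completeness is unknown. And the main sample shrinks: if all 43 organized cases were users (an assumption; 43 is not a planned sample size), 43 × (1 − p) leaves about 39, 32 and 21 or 22 at p = 10%, 25% and 50%. Where the effect arises at initiation, this loss is smaller than the dilution it removes. With similar variability in both groups, the ratio of effect to standard error falls by √(1 − p), that is 0.95, 0.87 and 0.71, instead of by about 0.90, 0.75 and 0.50.

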Non-diabetic Chronic Kidney Disease (CKD) poses a significant clinical challenge, with existing treatment methods having limitations [15]. Available approaches are primarily focused on managing the underlying causes of CKD, such as hypertension and proteinuria, to slow disease progression and prevent complications [16]. Common interventions include lifestyle changes, blood pressure control with Angiotensin-Converting Enzyme inhibitors (ACE inhibitors) or Angiotensin Receptor Blockers (ARBs), and the use of Sodium-Glucose Co-Transporter-2 inhibitors (SGLT2 inhibitors) in certain circumstances [17]. However, for CKD without diabetes mellitus (DM), there remains a vital need for novel treatment options for various reasons [1]. New therapies like finerenone show the potential for such advances. Finerenone is a non-steroidal mineralocorticoid receptor antagonist that has been shown to have benefits in studies on patients with CKD and type 2 diabetes, slowing CKD progression and providing cardiovascular protection [18]. Researchers and clinicians are hopeful that this treatment can also be successfully applied to non-diabetic CKD populations, hence there is interest in further research into its efficacy and safety in this particular group [19].

While current non-diabetic CKD treatment strategies include managing hypertension and proteinuria, there is a clear need for new treatment options [20]. Innovative therapies like finerenone that target specific mechanisms of CKD pathology have the potential to improve outcomes and meet the unmet needs of patients with CKD [21]. Further research and clinical trials

are necessary to explore and validate the efficacy and safety of these new therapeutic approaches [22].

Finerenone holds promise for diabetic CKD; however, the lack of evidence for its use in non-diabetic CKD underlines the importance of further clinical research in this area [23]. Such studies would be incredibly valuable for expanding treatment options and improving outcomes for a broader CKD patient population [24].

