Kidney-related indicators and cardiovascular events: including eGFR, serum creatinine levels, records of kidney disease events (such as renal function decline, initiation of dialysis, or kidney transplantation), and records of cardiovascular events.

Safety data: including all adverse events recorded.

(D) Data Collection and Data Management

Determine data sources:

The data will primarily be sourced from the hospital's electronic health record HIS system, which may include clinical records, medication administration records, laboratory test results, and radiological reports.

Acquisition of patient information:

Based on the study's inclusion and exclusion criteria, construct a query to compile a list of patients from the hospital database who meet the criteria for CKD.

Creation of data collection forms:

Create a standardized data collection form listing all the information that needs to be gathered.

Ensure the form includes all the key variable items involved in the study.

Data extraction:

Use the search and export functions of the EHR system to export the required data points for each patient involved in the study. This includes the patient's basic information, medication usage, laboratory test results, etc. For information that cannot be collected automatically, such as physicians' notes or qualitative descriptions in radiological reports, manually extract or enter these into the data tables.

Data entry and coding:

Enter the extracted data into the data collection forms. To protect patient privacy, encode patient information wherever possible to anonymize patient identity within the dataset. For qualitative data, such as diagnoses or symptom descriptions, develop a standardized coding system that converts them into quantitative data suitable for statistical analysis.

Quality control:

Perform data cleaning on the preliminary collected data, checking for missing data, outliers, and inconsistencies. Conduct data verification to ensure the accuracy and completeness of all data. If possible, have two research assistants perform data extraction and entry independently and reconcile any discrepancies.

Data storage and security:

Ensure that all electronic data is stored on secure, password-protected servers or cloud services. Regularly back up data to mitigate the risk of data loss.

Ethical compliance:

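### Dated background therapy and prior MRA use are not specified, so the effect of therapy started alongside finerenone may be attributed to finerenone, and would be in the unadjusted paired test

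*Combined protocol and SAP*

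**What the plan says.** **Eligibility (section IV(B)).** There are three inclusion criteria: attendance at the department from 15 December 2023, non-diabetic kidney disease, and an available electronic record. There are two exclusions: type 2 diabetes and refusal. None concerns background therapy, a change in it, or earlier MRA use.

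**Baseline (section IV(B)).** It is the occasion when the patient was "first admitted to the nephrology department for hospital treatment or an outpatient visit". It is not the date finerenone was started.

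**Variables (section IV(C)).** Medication appears under "Baseline patient characteristics: including age, gender, stage of kidney disease, comorbidities, medication history, etc". The one drug with its own entry is finerenone: "Use of finerenone: including dosage, duration of therapy, etc".

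**Data sources (section IV(D)).** The hospital system is the main source, "which may include clinical records, medication administration records, laboratory test results, and radiological reports". The data extraction paragraph adds medication usage to what is exported for each patient, without restricting it to baseline or to finerenone. It does not mention drug classes or dates.

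**Analysis (section V).** A before/after comparison, if made, may use a paired t-test or Wilcoxon signed-rank test. Multivariate regression and a Cox model are permitted as ways to adjust for confounding. Both are optional, and no confounder is named.

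**Background.** The protocol itself names ACE inhibitors and ARBs as common interventions, and SGLT2 inhibitors in some circumstances, within approaches intended to slow progression.

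**The concern.** The stated objective is to assess kidney disease progression after finerenone. The protocol names other drugs given for the same purpose, yet the variable list does not ask when they were started relative to finerenone.

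Two kinds of patient cause difficulty:

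- **Co-starters.** A patient who begins an SGLT2 inhibitor and finerenone together, after the baseline contact, is recorded as a finerenone patient with no SGLT2 inhibitor in the baseline history. Adjusting for baseline history cannot correct this.
- **Switchers.** A patient moved from another MRA may have a before value that already includes class effect. That pulls the before/after change towards zero.

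If either group is sizeable, the renal results could describe a combination, or a diluted contrast, and be reported as the effect of finerenone. The cardiovascular and safety results are open to the same misattribution.

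**Working it through.** The plan states no sample size, effect size, SD or error rate, so there is no figure of its own to reproduce. The check is to read the sections together and then give the form of the bias under declared assumptions.

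**1. Can the plan as written identify a co-start?** This needs the start date of the other drug and the start date of finerenone.
- Section IV(C) gives finerenone duration, and medication history at first contact.
- Section IV(D) may make the other dates obtainable, but does not specify them.
- Section V quantifies finerenone usage only.

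So the information may exist in the records, but no variable or analysis rule uses it.

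**2. Does the analysis remove a co-start effect?** The paired t-test and Wilcoxon test carry no covariates, so they cannot. The regression and Cox models could, but only if someone chooses to include co-therapy. A drug started during follow-up would also need time-varying handling, which is not mentioned.

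**3. Size of the shift (assumptions, not document figures).** Let c be the fraction co-starting a therapy that changes the eGFR slope by b, with no true finerenone effect. The sign of b is also an assumption; it is taken as positive below.

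- Single-arm: bias = c × b. With c from 30% to 60% and b from 1 to 2 mL/min/1.73 m² per year, the range is 0.3 × 1 = 0.3 to 0.6 × 2 = 1.2 mL/min/1.73 m² per year.
- With a control group: bias = (c_treated − c_control) × b. With 60% against 30% and b = 2, this is 0.3 × 2 = 0.6. With equal co-start rates it is zero, and with more co-starts among controls it reverses sign.

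**4. Switchers (assumption).** If a fraction s switch from an MRA with an identical class effect and no MRA-free gap, the measured before/after effect is multiplied by (1 − s). At s = 20% the factor is 1 − 0.2 = 0.8, a loss of one fifth.

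**5. What this does to the paired test (illustration).** The setting is 100,000 simulated data sets with a true finerenone effect of zero, an assumed two-sided 5% level, and n = 43. That n is the only patient count in the documents (section VIII: cases already organised, not a planned size). Each patient co-starts with probability f, and co-therapy shifts the paired change by d SD. The mean shift is f × d; for example 0.4 × 0.5 = 0.2 SD. The percentage of tests declaring a difference is:

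| d (SD) | f = 0 | 20% | 40% | 60% | 100% |
|---|---|---|---|---|---|
| 0.25 | 5.0 | 6.0 | 9.6 | 15.9 | 36.1 |
| 0.50 | 5.1 | 9.5 | 23.8 | 46.5 | 89.4 |
| 0.75 | 5.0 | 14.9 | 43.6 | 77.3 | 99.8 |

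The test holds its level when nobody co-starts. It loses it as f and d rise. Which cell applies cannot be learned from the documents.

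**The case against.** The strongest reply is that the plan is more open than the variable list suggests. Four parts of that reply have force.

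- **Medication is not confined to baseline history.** A reader of section IV(C) alone might infer that it is. Section IV(D) exports medication usage for each patient and names administration records as a possible source, and the lists in IV(C) are open-ended. This stands. What is missing is a specification of drug classes, dates and analytic use.
- **Misattribution is not certain.** A reader might infer that co-started therapy will necessarily be credited to finerenone. Section V permits multivariate and Cox adjustment, and the paired test is itself conditional. This also stands: the risk is certain only for the unadjusted paired test. Optional adjustment with no named covariates still gives no assurance that co-therapy will be included.
- **Prior MRA use could often be recovered.** Baseline medication history may well hold it, so many switchers could be identified. An MRA started between first contact and finerenone would be missed, and no analysis is planned for either case.
- **c × b is a single-arm formula.** Section V contemplates treatment and control groups, where only the difference in co-start rates matters.

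Nothing in the documents shows that any patient co-started a drug or switched from another MRA. That first nephrology contact is a time when therapy changes is a reasonable supposition, not a documented fact. In particular, a reader might take the significant preliminary differences reported for 43 cases as a product of co-therapy; the documents give no basis for saying so.

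**Conclusion.** The concern holds in a limited form. Eligibility sets no background-therapy or prior-MRA condition, dated co-therapy is not a specified variable, and adjustment is discretionary. Therapy started with or shortly before finerenone may therefore be counted as finerenone effect, and in the unadjusted paired comparison its whole average contribution would be.

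The size cannot be derived from the documents. The 0.3 to 1.2 mL/min/1.73 m² per year range, the factor of 0.8 and the simulated rejection rates all rest on assumed inputs and show only how the bias behaves. The annual slope is a convenient scale, not an endpoint that the plan states. The range applies to a single-arm comparison; with controls the bias may be smaller, absent or reversed. The factor of 0.8 further requires an identical class effect and no gap between the two MRAs.

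This should be settled before the main analysis, because it bears directly on the stated objective and the records may already hold what is needed.

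**What to change.** 1. **Extract dates.** From the medication usage data and medication administration records, take dated starts and stops of ACE inhibitor/ARB, SGLT2 inhibitor, other MRA, and steroid or immunosuppressive therapy. Anchor them to the finerenone start date; for comparators, use whatever index date the study defines.
2. **Flag.** Mark prior MRA use, and co-starts at or before index, within a look-back window that the sponsor states and justifies in advance.
3. **Adjust.** Replace reliance on the paired test with a regression of eGFR change that includes both flags. In a single-arm model, report the estimated change with both flags set to zero.
4. **Later starts.** Handle therapy begun after index as time-varying or in a sensitivity analysis. Do not enter it as a baseline covariate, since that conditions on events after treatment began.
5. **Restrict.** Repeat the main eGFR analysis in patients with no co-start and no prior MRA, and report both estimates with confidence intervals.
6. **Conclude.** Word the conclusion as finerenone with concurrent therapy unless the restricted estimate supports a finerenone-specific effect. State beforehand what would count as support, for example a restricted confidence interval that excludes no effect, because two estimates can differ by chance.

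The cost is more extraction and a smaller restricted set with a wider interval. If the records lack usable dates, report that as a limitation. The restriction addresses this source of bias only. The study is retrospective, so none of this alters patient care.

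### Safety is an objective, yet the only safety variable named is recorded adverse events; no laboratory safety outcome is prespecified although laboratory results are exported, so harms may be under-ascertained

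*Combined protocol and SAP*

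**What the plan says.** All references are to the combined protocol and SAP.

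- **Objective.** Section II pairs kidney disease progression with the safety profile of finerenone, and section III lists safety evaluation as one of three research items. The background, just before section II, extends the question to non-diabetic patients "including those with an estimated glomerular filtration rate (eGFR) below 15" ml/min/1.73m².
- **Safety variable.** Section IV(C) gives one line: "Safety data: including all adverse events recorded". No event list, definition, grading, laboratory threshold or time window follows.
- **Kidney variables.** The same section lists kidney and cardiovascular measures separately, "including eGFR, serum creatinine levels, records of kidney disease events (such as renal function decline, initiation of dialysis, or kidney transplantation". These are not labelled as safety data.
- **Sources.** Section IV(D) draws on the hospital's electronic record, "which may include clinical records, medication administration records, laboratory test results, and radiological reports". Of the export it says: "This includes the patient's basic information, medication usage, laboratory test results, etc". Notes are a supplement: "For information that cannot be collected automatically, such as physicians' notes or qualitative descriptions in radiological reports, manually extract".
- **Analysis.** Section V contains no analysis dedicated to adverse events. Its outcome examples are renal function and cardiovascular events.

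**The concern.** In a retrospective cohort, monitoring is whatever routine care provided. A laboratory abnormality becomes a recorded adverse event only if a clinician labels it as one or if a stated rule classifies it. The plan states no rule. Whether an event is counted may therefore depend on how often a patient was tested and how readily the clinician attributed the result to the drug.

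Two separate problems follow. First, absolute event rates in treated patients may be too low, which would make the drug look safer than it is. Second, if treated and untreated patients were ever compared on safety, unequal testing or recording would distort the contrast. It would inflate a harm if users were watched more closely and hide one if they were watched less. The plan already exports the data needed to reduce the first problem and to make the second visible, but assigns them no safety role.

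**Working it through.** **Step 1: set the sections side by side.** The plan states no event rate, detection rate, sample size or power, so it has no figure to reproduce. The check is first a reading of the text.

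- IV(C) names one safety variable, recorded adverse events.
- IV(D) exports the data points the study requires and builds its collection form from the key study variables. IV(C) is where those variables are set. A laboratory safety measure absent from IV(C) therefore need not reach the form.
- IV(C) does collect eGFR and creatinine, so for kidney function only the safety definition is missing.
- Section V adds no adverse-event analysis and no handling of how often patients were seen or tested.

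**Step 2: illustrate under-ascertainment.** Every input is an assumption. The number 43 is the count of cases organised so far (section VIII). The plan does not say that these are finerenone users or that 43 is a target size. True risks of 5%, 10% and 20% and recording fractions of 30% and 50% are chosen for illustration.

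Formulas: recorded risk = true risk × fraction recorded; expected recorded events = 43 × recorded risk; chance of recording none = (1 − recorded risk)^43.

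| True risk | True expected events | Recorded fraction | Expected recorded | Chance of none |
|---|---|---|---|---|
| 5% | 43 × 0.05 = 2.15 | 50% | 1.08 | 0.975^43 = 34% |
| 5% | 2.15 | 30% | 0.65 | 0.985^43 = 52% |
| 10% | 43 × 0.10 = 4.3 | 50% | 2.15 | 0.95^43 = 11% |
| 10% | 4.3 | 30% | 1.29 | 0.97^43 = 27% |
| 20% | 43 × 0.20 = 8.6 | 50% | 4.3 | 0.90^43 = 1.1% |
| 20% | 8.6 | 30% | 2.58 | 0.94^43 = 7% |

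For comparison, with every event recorded and a true risk of 10%, the chance of seeing none is 0.90^43 = 1.1%.

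**Step 3: illustrate a comparison, if one were made.** Apparent risk ratio = true risk ratio × (fraction detected in users ÷ fraction detected in non-users). The detection fractions are again assumed.

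- True ratio 1, detection 80% in users and 50% in non-users: 1 × 0.8/0.5 = 1.6.
- True ratio 2, same detection: 2 × 0.8/0.5 = 3.2.
- True ratio 2, detection 50% in users and 80% in non-users: 2 × 0.5/0.8 = 1.25.
- Equal detection of 50%: the ratio is unchanged, but each observed risk is halved (10% becomes 5%).

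The bias can therefore run in either direction. Its size simply restates the detection ratio that was assumed.

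**The case against.** The strongest reply is that the plan does not exclude laboratory events. The safety line begins with an inclusive word, the source is an electronic record that covers laboratory results, and notes are read by hand only where export fails. A reader might infer that safety is taken solely from clinicians' notes, but the text does not say so. Laboratory-based events are unspecified rather than ruled out. This corrects the description but does not close the gap, because without a rule an abnormal value is not an event.

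A reader might also infer that the plan compares users with non-users on safety. It does not state such a comparison. A control group appears once, conditionally, in the survival-analysis part of section V, with CKD progression as the example. It is never defined, and the before-after test in section V concerns renal function. Since no inclusion criterion requires finerenone use, non-users can enter the cohort, but a safety contrast remains a possibility only.

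Three further points stand:

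- The 43 cases are not shown to be exposed, and all rates in the illustration are assumed. Under-counting is a risk, not a demonstrated fact.
- Highest values and raw counts above a limit rise with the number of tests, so they would bring unequal detection back into a group comparison.
- Non-users have no index date. The study baseline is the first CKD admission or visit, not the start of the drug.

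Finally, the documents do not mention potassium. They say only that "Finerenone is a non-steroidal mineralocorticoid receptor antagonist", so the choice of analyte is for the investigators to confirm.

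**Conclusion.** The point holds in a limited form. Safety is a stated objective, the only safety variable named is recorded adverse events, and the exported laboratory results are given no safety definition, window or rule for testing frequency. Harms may therefore be under-ascertained, and any later user versus non-user safety comparison would be open to detection bias in either direction.

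The documents do not allow the size to be estimated. On assumed inputs (43 exposed, true risk 10%, 30-50% of events recorded), 4.3 expected events become 1.3-2.2, and the chance of recording none rises from about 1% to 11-27%. At true risks of 5% and 20% that chance is 34-52% and 1-7%. The documents do not show that harms have been missed or that recording differs between groups. The change is worth making because it is cheap and gives better ascertainment than IV(C) as written.

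**What to change.** Add laboratory safety outcomes to section IV(C), computed by one written rule from the existing export. For patients given finerenone, with time counted from the first dose:

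1. Change in eGFR from the last pre-treatment value to the value nearest a prespecified early time point. This uses data already collected.
2. Serum potassium at baseline and at the value nearest the same time point, and the proportion of tested patients with any value above the hospital laboratory's reporting limit. Potassium is proposed because of the drug class, so the investigators should confirm the analyte before extraction.
3. Alongside both, the number of tests, the number of patients never tested and the person-time.

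Fix the time point and its window before further data are extracted. Add a short adverse-event analysis to section V, and keep recorded adverse events as a separate descriptive source.

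Compare with non-users only if a comparator and a matching start date are defined. Use the same windows in both groups and show test frequency by group. Do not compare highest values or raw counts across groups without accounting for the number of tests.

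The cost is a few extra export fields and one table, and reported event rates may rise. A group comparison would cost more, because the plan does not yet define the comparator or the start date it needs.
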